3 OBJECTIVES AND ENDPOINTS

Zealand Pharma A/S

Objectives	Endpoints	
To assess the efficacy of dasiglucagon injection in children < 6 years of age with T1D	Primary endpoint is pharmacodynamics (PD): Plasma glucose change from baseline at 30 minutes after IMP injection or at the time of rescue by IV glucose Secondary endpoint is PD*: Plasma glucose change from baseline at 15 minutes after IMP injection or at the time of rescue by IV glucose	
To assess PK of dasiglucagon in children with T1D To assess the safety profile of dasiglucagon in children with T1D	 PK endpoints will be derived from plasma dasiglucagon profiles from 0 to 300 minutes*: Area under the plasma concentration versus time curve from 0 to 30 minutes post-dose (AUC_{0-30min}) AUC from 0 to 300 minutes post-dose (AUC_{0-300min}) AUC from 0 to the last time point with a measured concentration (AUC₀₋₁) AUC from 0 to infinity post-dose (AUC_{inf}) C_{max} Time to C_{max} Terminal elimination rate constant of plasma dasiglucagon (λ₂) Terminal plasma elimination half-life of dasiglucagon (t½) Total body clearance of plasma dasiglucagon (Cl/f) Volume of distribution of plasma dasiglucagon (MRT) AEs Administration of rescue IV glucose infusion within 30 minutes of IMP injection Time to first IV glucose infusion following treatment with dasiglucagon within 30 minutes 	
Other endpoints	Anti-drug antibodies	

Abbreviations: ADA=anti-drug antibodies; AE=adverse event; AUC=plasma concentration versus time curve; IMP=investigational medicinal product; IV=intravenous; PD=pharmacodynamics; PK=pharmacokinetics; T1D=Type 1 diabetes

^{*} as the sampling frequency for PK and PD will gradually be reduced with lower weight for children of 10 kg and below (as specified in Table 6-4), these marked endpoints will be assessed to the extent possible based on the samples obtained for the individual child.

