4.3 Justification for Dose

Dasiglucagon bolus dose of 0.6 mg SC has been approved by FDA for the treatment of severe hypoglycemia in pediatric and adult patients with diabetes aged 6 years and above. Based on population PK model predictions and Pop PK/PD Simulations (Study 20-046), the 0.6 mg dose is expected to be an appropriate dose in an older subset of children < 6 years and ≥ 2 years,

whereas a lower dose of 0.3 mg is expected to be an appropriate dose in a younger subset of children < 6 years. The results from the present trial will be used to determine the appropriate dose(s) for children < 6 years.

The rationale for the suggested split in doses between the 2 groups, which are partially overlapping, is to maximize the efficacy benefit in this vulnerable age group without any increase in untoward effects. Young children are more susceptible to low blood glucose and in addition to this, it has been shown that the frequency of severe hypoglycemia is one of the factors that has a negative impact on specific neuropsychological functions.

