6.5.2 Rescue Provisions for Hypoglycemia

During insulin-induced hypoglycemia, plasma glucose levels as well as the patient status will be monitored closely throughout the procedure. After administration of IMP (t=0), if their glucose levels become too low, patients may receive post-treatment IV glucose infusion to ameliorate hypoglycemia, as follows:

- The IV glucose infusion should be initiated if a patient experiences escalating symptoms
 of hypoglycemia (eg, start of moderate symptoms of hypoglycemia) at any time during
 the test procedure. Glucose infusion should then be initiated targeting a plasma glucose
 level >90 mg/dL.
- If plasma glucose is <70 mg/dL between t=8 and t=30 minutes, glucose infusion (eg, 1 to 2 mg/kg administered over 5 to 10 seconds) should be initiated to maintain plasma glucose between 70 mg/dL (inclusive) and 90 mg/dL. Pause glucose infusion if plasma glucose is >90 mg/dL.
- If plasma glucose is <90 mg/dL at t≥30 minutes, glucose infusion (eg, 2 to 3 mg/kg administered over 5 to 10 seconds) should be initiated. Pause glucose infusion when plasma glucose is >90 mg/dL.

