- Plasma glucose using glucose analyzer during induction of hypoglycemia and until 300 minutes after dosing. Plasma glucose levels must be checked by glucose analyzer approximately every 10 minutes while glucose levels are above 110 mg/dL (6.1 mmol/L), and approximately every 5 minutes once glucose levels are at or below 110 mg/dL (6.1 mmol/L). Plasma glucose should be confirmed by the glucose analyzer prior to the pre-dose PK and PD samples and prior to the administration of dasiglucagon. After dosing with dasiglucagon, once glucose levels reach ≥110 mg/dL (6.1 mg/dL), glucose levels should be checked approximately every 30 minutes until 300 minutes.
- Glucose levels using CGM during induction of hypoglycemia and until 300 minutes after dosing. Dexcom 6 will be fitted in the morning at Visit 2 and must remain fitted until 300 minutes after IMP administration.
- Administration of IMP (during hypoglycemic clamp procedure)

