9.4.3.3 Safety and Tolerability Endpoints

Clinical Laboratory Data

Clinical laboratory test results will be marked whether the result is below, within or above the respective reference range. The number of values outside of the reference range will be counted.

AEs

AEs will be coded using the latest available version of the Medical Dictionary for Regulatory Activities. All AEs will be listed, however only AEs that are considered treatment emergent (AEs with an onset time at or after the initial dose of trial drug) will be tabulated. Such tables will include the counts and percentages of patients experiencing AEs by system organ class and preferred term. If a patient has more than 1 AE which codes to the same preferred term, the patient will be counted only once for that preferred term. The total number of events documented per system organ class and preferred term will also be displayed.

Other Safety Data

Administration and time to first IV glucose infusion, within 30 minutes after IMP administration (NB: IV glucose infusion prior to IMP administration should not be included, as it is part of hypoglycemic clamp procedure) will be described with descriptive statistics.

Vital signs, physical examination results, ECG, and local tolerability data will be summarized with descriptive statistics.

Immunogenicity

Occurrence of ADA will be analyzed descriptively. ADA and result from associated characterization assays will be presented descriptively.

Continuous Glucose Monitoring (CGM)

At Visit 2, glucose levels will be monitored by CGM.

CGM data will be presented graphically as individual plots of glucose measurements over time from the time of stopping the participant's insulin pump to 300 minutes after dasiglucagon administration.

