14.1.2 Hypoglycemia Induction Procedure

A summary table will be prepared summarizing the data collected for the hypoglycemia induction procedure. Frequency counts and percentages will be presented for the number of patients where the hypoglycemia induction procedure was performed and for the number of patients where glucose was administered intravenously prior to dosing.

The duration in minutes between stop of insulin pump (respectively for multiple daily injections (MDI) users, last basal dose before the Hypoglycaemia procedure) and time when Hypoglycaemia procedure was initiated will be calculated and summarized.

Descriptive statistics will be given for the total amount of insulin administered to induce hypoglycemia and the total amount of glucose administered during the induction procedure.

All details related to the hypoglycemia induction procedure will be provided in a listing.

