14.3.5 Extent of Exposure

**Table 14.3.5.1 Hypoglycemia Induction Procedure
 Safety Analysis Set**

| | dasiglucagon 0.3mg (N=XX) | dasiglucagon 0.6mg (N=XX) | Total (N=XX) |
|--|------------------------------|------------------------------|-----------------|
| Hypoglycemia induction procedure performed? | | | |
| Yes | xx (xx.x%) | xx (xx.x%) | xx (xx.x%) |
| No | xx (xx.x%) | xx (xx.x%) | xx (xx.x%) |
| MDI User: Duration between last basal dose before the hypoglycemia procedure and time when hypoglycemia procedure was initiated (min) | | | |
| n | xx | xx | xx |
| Mean (SD) | xx.x (xx.xx) | xx.x (xx.xx) | xx.x (xx.xx) |
| Median | xx.x | xx.x | xx.x |
| Min, Max | xx, xx | xx, xx | xx, xx |
| Pump User: Duration between stop of insulin pump and time when hypoglycemia procedure was initiated (min) | | | |
| n | xx | xx | xx |
| Mean (SD) | xx.x (xx.xx) | xx.x (xx.xx) | xx.x (xx.xx) |
| Median | xx.x | xx.x | xx.x |
| Min, Max | xx, xx | xx, xx | xx, xx |
| Total amount of insulin administered to induce hypoglycemia (IU) | | | |
| n | xx | xx | xx |
| Mean (SD) | xx.x (xx.xx) | xx.x (xx.xx) | xx.x (xx.xx) |
| Median | xx.x | xx.x | xx.x |
| Min, Max | xx, xx | xx, xx | xx, xx |
| Glucose administered intravenously prior to dosing? | | | |
| Yes | xx (xx.x%) | xx (xx.x%) | xx (xx.x%) |
| No | xx (xx.x%) | xx (xx.x%) | xx (xx.x%) |
| Total amount of glucose administered (mL) | | | |
| n | xx | xx | xx |
| Mean (SD) | xx.x (xx.xx) | xx.x (xx.xx) | xx.x (xx.xx) |
| Median | xx.x | xx.x | xx.x |
| Min, Max | xx, xx | xx, xx | xx, xx |

| | dasiglucagon 0.3mg (N=XX) | dasiglucagon 0.6mg (N=XX) | Total (N=XX) |
|---|------------------------------|------------------------------|-----------------|
| Rescue IV Glucose given after dosing? | | | |
| Yes | xx (xx.x%) | xx (xx.x%) | xx (xx.x%) |
| No | xx (xx.x%) | xx (xx.x%) | xx (xx.x%) |
| Time to first IV glucose infusion (min) | | | |
| n | xx | xx | xx |
| Mean (SD) | xx.x (xx.xx) | xx.x (xx.xx) | xx.x (xx.xx) |
| Median | xx.x | xx.x | xx.x |
| Min, Max | xx, xx | xx, xx | xx, xx |

Time to first IV glucose infusion (min): Time of start of first glucose administration - Time of administration of study medication.

Source: xxx

PROGRAM SOURCE: xxx.sas, DATA CUT-OFF DATE: DDMMYYYY

RUN DATE: DDMMYYYY hh:mm

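### The SAP's rescue-glucose rows drop the 30-minute window that the protocol sets for both rescue safety endpoints

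*SAP*

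**What the plan says.** Protocol section 3 lists as a safety endpoint "Administration of rescue IV glucose infusion within 30 minutes of IMP injection", followed by the time to first IV glucose with the same 30-minute limit. The synopsis repeats both. Protocol 9.4.3.3 applies the window again in the analysis text and excludes pre-dose glucose: "time to first IV glucose infusion, within 30 minutes after IMP administration (NB: IV glucose infusion prior to IMP administration should not be included".

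The SAP summarises rescue and its timing in one table, shell Table 14.3.5.1 (Hypoglycemia Induction Procedure). Its row reads "Rescue IV Glucose given after dosing" with Yes/No counts. Below it is a time row with this footnote: "Time to first IV glucose infusion (min): Time of start of first glucose administration - Time of administration of study medication". No row label, footnote or programming note mentions 30 minutes. SAP 14.1.2, the text behind the table, provides counts "for the number of patients where glucose was administered intravenously prior to dosing" and says nothing about rescue after dosing. SAP 15 states that nothing in the protocol-specified analysis was changed.

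**The concern.** The window is part of the endpoint definition, and the SAP leaves it out without saying so. Glucose after 30 minutes is foreseen. Protocol 6.5.2 provides: "If plasma glucose is <90 mg/dL at t≥30 minutes, glucose infusion" is to be started, with no upper time limit. Protocol 8.1.2 keeps monitoring going: "glucose levels should be checked approximately every 30 minutes until 300 minutes".

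Late glucose is also a different kind of event. Under 6.5.2 the glucose trigger is below 70 mg/dL between 8 and 30 minutes but below 90 mg/dL from 30 minutes on, so an unlimited row pools infusions started under two thresholds.

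The table is split by dose, and protocol 4.3 says: "The results from the present trial will be used to determine the appropriate" dose or doses for children under 6. No rule ties the rescue rate to that choice, but with 4 children per dose a single reclassified child is conspicuous.

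**Working it through.** The plan gives no figure for this point, so the check is a comparison of texts, followed by the arithmetic for scale.

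**Comparison**

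| Feature | Protocol (3; 9.4.3.3) | SAP Table 14.3.5.1 |
|---|---|---|
| Rescue given: upper limit | 30 min after dosing | none |
| Time to first glucose: upper limit | 30 min after dosing | none |
| Pre-dose glucose | excluded | excluded by the label of the Yes/No row; not excluded by the time-row footnote |
| Definition in SAP text | not applicable | none (14.1.2 covers pre-dose glucose only) |
| Declared change (SAP 15) | not applicable | none |

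The SAP does use a before-30-minutes condition in 10.1 and 11.1, but it belongs to the primary plasma glucose endpoint and does not carry over to this table.

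**Effect on the rescue rate.** Inputs are 4 children per dose and 8 in total (protocol 4.1; SAP 4). Let k be the number of children in one dose group whose first post-dose glucose starts after 30 minutes. Each is Yes in the SAP row and No under the protocol endpoint, so the rate rises by k/4 in that dose column and k/8 in the Total column.

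- k = 1: 1/4 = 25 points by dose; 1/8 = 12.5 points overall.
- k = 2: 2/4 = 50 points by dose; 2/8 = 25 points overall.

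**Effect on the time row.** The protocol's time endpoint cannot exceed 30 minutes. The row as written can hold values up to the end of monitoring at 300 minutes, and 300/30 = 10. This is a ceiling, not an expected value.

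**How likely is late glucose?** The documents give no rate. The planning figures in protocol 9.2 (6 to 11 years; mean rise at 30 minutes 96 mg/dL, SD 20) allow a rough check on the 90 mg/dL trigger at 30 minutes for baselines of 70 to 90 mg/dL:

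- Baseline 70: rise to 90 is 20, so (96 − 20)/20 = 3.8 SD below the mean.
- Baseline 90: rise to 90 is 0, so (96 − 0)/20 = 4.8 SD below the mean.

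If younger children respond as the older ones did, the trigger at exactly 30 minutes should rarely be met. Late glucose would have to come from a later fall, from a different response in children under 6, or from escalating symptoms, for which 6.5.2 allows glucose at any time.

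**Footnote.** It refers to the first glucose administration without saying post-dose, in a table that also summarises pre-dose glucose. Protocol 6.5.1 bars glucose within 30 minutes before dosing. Read literally, a child given glucose during induction would therefore contribute a time of −30 minutes or less. This is a secondary point and affects the time row only.

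**The case against.** The strongest reply is that the Yes/No row is labelled truthfully. It claims any rescue after dosing, so what is missing is a windowed row, and nothing false is reported. With 4 children per dose, a maximum above 30 in the time row would reveal a late start. Protocol 8.3.6 makes post-dose IV glucose a reportable adverse event, and the adverse event listing carries start times, so a reader could largely recover the 30-minute status by inspection. Tables 14.2.3.1 and 14.2.3.2 also restrict to children without rescue, which gives an indirect count. Late IV rescue is made less likely because children may eat from 35 minutes and take usual meals from 2 hours. A negative time would be an obvious programming error.

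Much of this is fair and limits the size of the point. It does not remove it. Two endpoints named in the protocol should come out of the planned tables, without being reconstructed from listings, and the no-rescue tables state no window either. The footnote wording is indeed a tidy-up, and the link to dose choice is general.

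**Conclusion.** The point holds. As written, Table 14.3.5.1 does not produce either of the protocol's two 30-minute rescue endpoints, and the departure is not declared. If any first post-dose infusion starts after 30 minutes, the rescue rate exceeds the protocol's by 25 percentage points per child in a dose group and 12.5 points overall, and the time summary includes values outside the endpoint's range. If no child has late or pre-dose glucose, the two versions coincide. These sizes assume the planned 4 children per dose; how often late glucose will occur cannot be derived from the documents. The primary endpoint is unaffected. The correction should be made, but the trial's main result does not depend on it.

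**What to change.** - In SAP 14.1.2 and Table 14.3.5.1, define both endpoints from the first IV glucose infusion started after dosing and within 30 minutes. Report n/N by dose and for the Total.
- State how a start at exactly 30 minutes is classified. The safety endpoints say within 30 minutes, the primary endpoint says before 30 minutes (protocol 9.4.2; SAP 10.1), and the two glucose triggers in protocol 6.5.2 both include the 30-minute point. These passages need to be reconciled.
- Show glucose first started after 30 minutes on a separate, labelled row, so that no safety information is lost.
- Add post-dose to the time-row footnote.
- If the wider window is intended, declare it in SAP 15.
- Align the table number: the index in SAP Appendix B lists this table as 14.3.5.2, the shell as 14.3.5.1.

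The cost is two derivation lines, one footnote word, one table row and a corrected number. No new data are needed.

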14.3.6 Other Safety Data

Figure 14.3.6.1 Continuous Glucose Monitoring - Individual Glucose Concentration-time Profiles
Safety Analysis Set

| | |
|-------------------------------|--|
| Type of Graph: | Individual Patient concentration-time profiles |
| x-Axis | Actual time from the time of stopping patient's insulin pump (h) |
| x-Axis label | Actual time from the time of stopping patient's insulin pump (h) |
| y-Axis | Use linear scale Use same scaling of y axis for all patients |
| y-Axis Label | Glucose concentration (mg/dL) Secondary y axis: mmol/L Results are converted into the unit 'mmol/L' by using the conversion factor 0.0555 (i.e. Glucose [mmol/L]=Glucose [mg/dL] *0.0555). |
| Additional Information | See next page for mock. |
| Notes | Panel Plot, separate panel for each dosing group. One page per subject. |
| Footnotes | Glucose-time profiles based on continuous glucose monitoring from the time of stopping the patient's insulin pump to 300 minutes after dasiglucagon administration. |

Programming Notes:

[figure not shown]
QC dataset will consist of reproducing the results plotted.

So, produce a dataset with

- TRTP
- USUBJID
- ARELTM
- AVAL (where PARAMCD=GLUCMG)
- AVAL (where PARAMCD=GLUCMOL)

QC Dataset to be sorted by trtpn, usubjid, areltm

Treatment=dasiglucagon 0.3mg

**Figure 14.3.6.2 Glucose Analyser Data- Individual Glucose Concentration-time Profiles
 Safety Analysis Set**

| | |
|-------------------------------|---|
| Type of Graph: | Individual Patient concentration-time profiles |
| x-Axis | Relative time from start of first dosing of IMP |
| x-Axis label | Actual time from the time of first dosing (min) |
| y-Axis | Use linear scale Use same scaling of y axis for all patients |
| y-Axis Label | Glucose Analyser concentration (mg/dL) |
| Additional Information | Similar layout as plot as figure 14.3.6.1 using Glucose analyser data and only one y-axis |
| Notes | Panel Plot, separate panel for each dosing group |
| Footnotes | Glucose-time profiles based on Glucose Analyser Data. |

Programming Notes:

QC dataset will consist of reproducing the results plotted.

So, produce a dataset with

- **TRTP**
- **USUBJID**
- **ARELTM**
- **AVAL**

QC Dataset to be sorted by trtpn, usubjid, areltm

17.1.1.1 14.3.6.3 Laboratory Data

**Table 14.3.6.3.1 Hematology Results
 Safety Analysis Set**

| Lab parameter (unit) | dasiglucagon 0.3mg (N=XX) | | dasiglucagon 0.6mg (N=XX) | | Total (N=XX) | |
|-----------------------------|------------------------------|----------------------|------------------------------|----------------------|-----------------|----------------------|
| | Value | Change from baseline | Value | Change from baseline | Value | Change from baseline |
| Lab parameter (unit) | | | | | | |
| Baseline | | | | | | |
| n | xx | | xx | | xx | |
| Mean (SD) | xx.x (xx.xx) | | xx.x (xx.xx) | | xx.x (xx.xx) | |
| Median | xx.x | | xx.x | | xx.x | |
| Min, Max | xx, xx | | xx, xx | | xx, xx | |
| Follow-up | | | | | | |
| n | xx | xx | xx | xx | xx | xx |
| Mean (SD) | xx.x (xx.xx) | xx.x (xx.xx) | xx.x (xx.xx) | xx.x (xx.xx) | xx.x (xx.xx) | xx.x (xx.xx) |
| Median | xx.x | xx.x | xx.x | xx.x | xx.x | xx.x |
| Min, Max | xx, xx | xx, xx | xx, xx | xx, xx | xx, xx | xx, xx |
| ... | | | | | | |

Baseline is the last assessment prior to study drug administration.

Source: xxx

PROGRAM SOURCE: xxx.sas, DATA CUT-OFF DATE: DDMMYYYY

RUN DATE: DDMMYYYY hh:mm

Programming Note:

- 2) In general present mean to 1 decimal more than individual data, STD to 2 decimals more than individual data. Refer to SAP
- 3) Order parameters alphabetically

**Table 14.3.6.3.2 Hematology Results – Reference Range Analysis
 Safety Analysis Set**

| Lab parameter (unit) | dasiglucagon 0.3mg (N=XX) | dasiglucagon 0.6mg (N=XX) | Total (N=XX) |
|----------------------|------------------------------|------------------------------|-----------------|
| Time point | | | |
| Lab parameter (unit) | | | |
| Baseline | | | |
| Low | xx (xx.x%) | xx (xx.x%) | xx (xx.x%) |
| Normal | xx (xx.x%) | xx (xx.x%) | xx (xx.x%) |
| High | xx (xx.x%) | xx (xx.x%) | xx (xx.x%) |
| Follow-up | | | |
| Low | xx (xx.x%) | xx (xx.x%) | xx (xx.x%) |
| Normal | xx (xx.x%) | xx (xx.x%) | xx (xx.x%) |
| High | xx (xx.x%) | xx (xx.x%) | xx (xx.x%) |
| ... | | | |

Baseline is the last assessment prior to study drug administration.

Source: xxx
 PROGRAM SOURCE: xxx.sas, DATA CUT-OFF DATE: DDMMYYYY

RUN DATE: DDMMYYYY hh:mm

Programming Note:

- 1) *Summarize the counts and percentages of the results above/below/within the reference range, for each parameter at each visit.*

Zealand Pharma A/S
ZP4207-21052
Zealand Pharma A/S
Protocol Number: ZP4207-21052

Statistical Analysis Plan
2-Jan-25
Clinical Study Report
Page x of y

**Table 14.3.6.3.3 Chemistry Results
Safety Analysis Set**

Baseline is the last assessment prior to study drug administration.
Results reported as below the detection limit are set to missing in this table.

Source: xxx
PROGRAM SOURCE: xxx.sas, DATA CUT-OFF DATE: DDMMYYYY

RUN DATE: DDMMYYYY hh:mm

Programming Note:

- 3) Repeat of Table 14.3.6.3.1 for Chemistry parameters
- 4) In general present mean to 1 decimal more than individual data, STD to 2 decimals more than individual data. Refer to SAP
- 5) Order parameters alphabetically

**Table 14.3.6.3.4 Chemistry Results – Reference Range Analysis
Safety Analysis Set**

Baseline is the last assessment prior to study drug administration.

Source: xxx

PROGRAM SOURCE: xxx.sas, DATA CUT-OFF DATE: DDMMYYYY

RUN DATE: DDMMYYYY hh:mm

Programming Note:

- 1) Repeat of Table 14.3.6.3.2 for Chemistry parameters
- 2) Summarize the counts and percentages of the results above/below/within the reference range, for each parameter at each visit.

**Table 14.3.6.3.5 Coagulation Results
Safety Analysis Set**

Baseline is the last assessment prior to study drug administration.

Source: xxx

PROGRAM SOURCE: xxx.sas, DATA CUT-OFF DATE: DDMMYY

RUN DATE: DDMMYY hh:mm

Programming Note:

- 1) Repeat of Table 14.3.6.3.1 for Chemistry parameters
- 2) In general present mean to 1 decimal more than individual data, STD to 2 decimals more than individual data. Refer to SAP
- 3) Order parameters alphabetically

**Table 14.3.6.3.6 Coagulation Results – Reference Range Analysis
Safety Analysis Set**

Baseline is the last assessment prior to study drug administration.

Source: xxx

PROGRAM SOURCE: xxx.sas, DATA CUT-OFF DATE: DDMMYYYY

RUN DATE: DDMMYYYY hh:mm

Programming Note:

- 1) *Repeat of Table 14.3.6.3.3 for Chemistry parameters*
- 2) *Summarize the counts and percentages of the results above/below/within the reference range, for each parameter at each visit.*

**Table 14.3.6.3.7 Immunogenicity
 Safety Analysis Set**

| | dasiglucagon 0.3mg (N=XX) | dasiglucagon 0.6mg (N=XX) | Total (N=XX) |
|--------------------------|---|---|----------------------------|
| Occurrence of ADA | | | |
| No | xx (xx.x%) | xx (xx.x%) | xx (xx.x%) |
| Yes | xx (xx.x%) | xx (xx.x%) | xx (xx.x%) |
| Missing | xx (xx.x%) | xx (xx.x%) | xx (xx.x%) |

Overall ADA including treatment-induced ADA and treatment-boosted ADA.
 Percentages is derived from patients having an ADA assessment.

Source: xxx
 PROGRAM SOURCE: xxx.sas, DATA CUT-OFF DATE: DDMMYYYY

RUN DATE: DDMMYYYY hh:mm

Table 14.3.6.4 Vital Signs
Safety Analysis Set

| Vital signs parameter (unit) | dasiglucagon 0.3mg (N=XX) | | dasiglucagon 0.6mg (N=XX) | | Total (N=XX) | |
|------------------------------|------------------------------|--------------|------------------------------|--------------|----------------------|--------------|
| | Time point | Value | Change from baseline | Value | Change from baseline | Value |
| Vital signs parameter (unit) | | | | | | |
| Screening | | | | | | |
| n | | xx | | xx | | xx |
| Mean (SD) | | xx.x (xx.xx) | | xx.x (xx.xx) | | xx.x (xx.xx) |
| Median | | xx.x | | xx.x | | xx.x |
| Min, Max | | xx, xx | | xx, xx | | xx, xx |
| Baseline | | | | | | |
| n | | xx | | xx | | xx |
| Mean (SD) | | xx.x (xx.xx) | | xx.x (xx.xx) | | xx.x (xx.xx) |
| Median | | xx.x | | xx.x | | xx.x |
| Min, Max | | xx, xx | | xx, xx | | xx, xx |
| Dosing: 30 minutes post-dose | | | | | | |
| n | xx | xx | xx | xx | xx | xx |
| Mean (SD) | xx.x (xx.xx) | xx.x (xx.xx) | xx.x (xx.xx) | xx.x (xx.xx) | xx.x (xx.xx) | xx.x (xx.xx) |
| Median | xx.x | xx.x | xx.x | xx.x | xx.x | xx.x |
| Min, Max | xx, xx | xx, xx | xx, xx | xx, xx | xx, xx | xx, xx |
| ... | | | | | | |
| Interpretation | | | | | | |
| Baseline | | | | | | |
| Normal | xx (xx.x%) | xx (xx.x%) | xx (xx.x%) | xx (xx.x%) | xx (xx.x%) | xx (xx.x%) |
| Abnormal (NCS) | xx (xx.x%) | xx (xx.x%) | xx (xx.x%) | xx (xx.x%) | xx (xx.x%) | xx (xx.x%) |
| Abnormal (CS) | xx (xx.x%) | xx (xx.x%) | xx (xx.x%) | xx (xx.x%) | xx (xx.x%) | xx (xx.x%) |
| ... | | | | | | |

Baseline is the last assessment prior to study drug administration.

Source: xxx

PROGRAM SOURCE: xxx.sas, DATA CUT-OFF DATE: DDMMYYYY

RUN DATE: DDMMYYYY hh:mm

Programming Note:

- 1) In general present mean to 1 decimal more than individual data, STD to 2 decimals more than individual data.
- 2) Order parameters as follows: Height, Weight, BMI, Temperature, Systolic BP, Diastolic BP, Pulse, Interpretation.
- 3) Continue for each parameter at screening, baseline and each post-baseline assessment
- 4) Start a new page after each parameter

Table 14.3.6.5 ECG Data
 Safety Analysis Set

| ECG parameter (unit) | dasiglucagon 0.3mg (N=XX) | dasiglucagon 0.6mg (N=XX) | Total (N=XX) |
|----------------------|------------------------------|------------------------------|-----------------|
| Time point | | | |
| ECG parameter (unit) | | | |
| Screening | | | |
| n | xx | xx | xx |
| Mean (SD) | xx.x (xx.xx) | xx.x (xx.xx) | xx.x (xx.xx) |
| Median | xx.x | xx.x | xx.x |
| Min, Max | xx, xx | xx, xx | xx, xx |
| ... | | | |
| Interpretation | | | |
| Screening | | | |
| Normal | xx (xx.x%) | xx (xx.x%) | xx (xx.x%) |
| Abnormal (NCS) | xx (xx.x%) | xx (xx.x%) | xx (xx.x%) |
| Abnormal (CS) | xx (xx.x%) | xx (xx.x%) | xx (xx.x%) |
| ... | | | |

Percentages are based on the total number of patients in the safety analysis set.

Source: xxx
 PROGRAM SOURCE: xxx.sas, DATA CUT-OFF DATE: DDMMYYYY

RUN DATE: DDMMYYYY hh:mm

Programming Note:

- 1) In general present mean to 1 decimal more than individual data, STD to 2 decimals more than individual data.
- 2) Order parameters as follows: Mean Heart Rate, PR Interval, QRS, QT, QTc, QTcF, and Interpretation.

